### 10.1.2. Investigator-Identified Rash Events of Special Interest and Gastrointestinal Abdominal-Related Adverse Events

The following is a primary endpoint for Parts 2 and 3:

• The proportion of subjects with a treatment-emergent, treatment-related AE consistent with a drug rash

All rashes, regardless of assessed causality or severity are reported as events of special interest by investigators in a protocol defined manner. However, the endpoint of interest is the proportion of subjects with a treatment-emergent, treatment-related AE consistent with drug rash.

Gastrointestinal (GI) abdominal-related TEAEs are also of interest, although these are not TEAEs of special interest for investigator reporting purposes. There are no appropriate standardized MedDRA queries in MedDRA to evaluate abdominal-related AEs that are appropriate to assess potential adverse events associated with BCX7353 use. To create a list of PTs that are pertinent, the events to be analyzed have been prospectively defined as all PTs within the MedDRA 19.1 hierarchy under the High-Level Group Terms (HLGTs) of 1) GI signs and symptoms; and 2) GI motility and defecation conditions. See Section 17 for a detailed list of PTs, High Level Terms, and HLGTs. This selection is broad enough so that GI events are appropriately identified and analyzed but excludes terms that, although in the GI SOC, are not representative of the events of concern such as oral or esophageal events.

For the investigator-identified rashes and the GI abdominal-related events, separate listings will be provided. In addition, for both investigator-identified rashes and GI abdominal-related events there will be a summary that shows, by treatment group, the number and percentage of subjects with:

- A TEAE
- A drug-related TEAE
- Permanent discontinuation from study drug due to the TEAE
- An AE that was considered an TESAE
- Any Grade 3 or higher TEAE
- Any Grade 3 or higher drug-related TEAE
- Any TEAE leading to interruption of study drug
- An TEAE that was considered a drug-related TESAE
- A TEAE that required use of concomitant medication

For treatment-emergent investigator-identified rashes and GI abdominal-related AEs, time to development of the TEAE will be estimated using the Kaplan-Meier method. The results will be displayed in summary tables as well as in a Kaplan-Meier plot. Subjects who do not experience the event of interest will be censored at the date of the last dose. Summary displays for the investigator-identified rashes and GI abdominal-related TEAEs will include a count of the number of TEAEs as well as the number of subjects who experience each TEAE.

A Kaplan-Meier plot and summary of duration of event will be provided for the investigator-identified rashes and GI abdominal-related TEAEs. The summary display will provide the median duration of event by treatment group, with the event as the unit of interest rather than the subject.

A separate analysis will be conducted in which the number and proportion of subjects with either a GI abdominal-related TEAE or an unconfirmed abdominal-only attack is presented. The number of events will also be included in the summary.

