10067715	Gastrointestinal sounds abnormal	Abdominal findings abnormal	Gastrointestinal signs and symptoms	Gastrointestinal disorders

Code	Preferred Term (PT)	High Level Term (HLT)	High Level Group Term (HLGT)	SOC
10075724	Gastrointestinal wall thickening	Gastrointestinal signs and symptoms NEC	Gastrointestinal signs and symptoms	Gastrointestinal disorders
10075726	Gastrointestinal wall thinning	Gastrointestinal signs and symptoms NEC	Gastrointestinal signs and symptoms	Gastrointestinal disorders
10021746	Infantile colic	Gastrointestinal and abdominal pains (excl oral and throat)	Gastrointestinal signs and symptoms	Gastrointestinal disorders
10063338	Infantile spitting up	Nausea and vomiting symptoms	Gastrointestinal signs and symptoms	Gastrointestinal disorders
10075315	Infantile vomiting	Nausea and vomiting symptoms	Gastrointestinal signs and symptoms	Gastrointestinal disorders
10073530	Intestinal calcification	Gastrointestinal signs and symptoms NEC	Gastrointestinal signs and symptoms	Gastrointestinal disorders
10065611	Intestinal congestion	Gastrointestinal signs and symptoms NEC	Gastrointestinal signs and symptoms	Gastrointestinal disorders
10067576	Malignant dysphagia	Gastrointestinal signs and symptoms NEC	Gastrointestinal signs and symptoms	Gastrointestinal disorders
10028140	Mucous stools	Faecal abnormalities NEC	Gastrointestinal signs and symptoms	Gastrointestinal disorders
10069369	Myochosis	Gastrointestinal signs and symptoms NEC	Gastrointestinal signs and symptoms	Gastrointestinal disorders
10028813	Nausea	Nausea and vomiting symptoms	Gastrointestinal signs and symptoms	Gastrointestinal disorders
10053634	Oesophageal discomfort	Gastrointestinal signs and symptoms NEC	Gastrointestinal signs and symptoms	Gastrointestinal disorders
10065567	Oesophageal food impaction	Gastrointestinal signs and symptoms NEC	Gastrointestinal signs and symptoms	Gastrointestinal disorders
10030180	Oesophageal pain	Gastrointestinal and abdominal pains (excl oral and throat)	Gastrointestinal signs and symptoms	Gastrointestinal disorders

Code	Preferred Term (PT)	High Level Term (HLT)	High Level Group Term (HLGT)	SOC
10034647	Peristalsis visible	Gastrointestinal signs and symptoms NEC	Gastrointestinal signs and symptoms	Gastrointestinal disorders
10057030	Pneumatosis intestinalis	Gastrointestinal signs and symptoms NEC	Gastrointestinal signs and symptoms	Gastrointestinal disorders

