10062879	Gastrooesophag eal sphincter insufficiency	Gastrointestinal atonic and hypomotility disorders NEC	Gastrointestinal motility and defaecation conditions	Gastrointestinal disorders
10021333	Ileus paralytic	Non-mechanical ileus	Gastrointestinal motility and defaecation conditions	Gastrointestinal disorders
10021335	Ileus spastic	Non-mechanical ileus	Gastrointestinal motility and defaecation conditions	Gastrointestinal disorders

Code	Preferred Term (PT)	High Level Term (HLT)	High Level Group Term (HLGT)	SOC
10021518	Impaired gastric emptying	Gastrointestinal atonic and hypomotility disorders NEC	Gastrointestinal motility and defaecation conditions	Gastrointestinal disorders
10059158	Infrequent bowel movements	Gastrointestinal atonic and hypomotility disorders NEC	Gastrointestinal motility and defaecation conditions	Gastrointestinal disorders
10022642	Intestinal dilatation	Gastrointestinal atonic and hypomotility disorders NEC	Gastrointestinal motility and defaecation conditions	Gastrointestinal disorders
10023003	Irritable bowel syndrome	Gastrointestinal spastic and hypermotility disorders	Gastrointestinal motility and defaecation conditions	Gastrointestinal disorders
10027110	Megacolon	Non-mechanical ileus	Gastrointestinal motility and defaecation conditions	Gastrointestinal disorders
10072286	Narcotic bowel syndrome	Non-mechanical ileus	Gastrointestinal motility and defaecation conditions	Gastrointestinal disorders
10058934	Neonatal intestinal dilatation	Gastrointestinal atonic and hypomotility disorders NEC	Gastrointestinal motility and defaecation conditions	Gastrointestinal disorders
10076953	Obstructive defaecation	Gastrointestinal atonic and hypomotility disorders NEC	Gastrointestinal motility and defaecation conditions	Gastrointestinal disorders
10030136	Oesophageal achalasia	Gastrointestinal dyskinetic disorders	Gastrointestinal motility and defaecation conditions	Gastrointestinal disorders
10071554	Oesophageal atony	Gastrointestinal atonic and hypomotility disorders NEC	Gastrointestinal motility and defaecation conditions	Gastrointestinal disorders
10067752	Oesophageal hypomotility	Gastrointestinal atonic and hypomotility disorders NEC	Gastrointestinal motility and defaecation conditions	Gastrointestinal disorders

Code	Preferred Term (PT)	High Level Term (HLT)	High Level Group Term (HLGT)	SOC

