10072419	Oesophageal motility disorder	Gastrointestinal dyskinetic disorders	Gastrointestinal motility and defaecation conditions	Gastrointestinal disorders
10030184	Oesophageal spasm	Gastrointestinal spastic and hypermotility disorders	Gastrointestinal motility and defaecation conditions	Gastrointestinal disorders
10060696	Presbyoesophag us	Gastrointestinal dyskinetic disorders	Gastrointestinal motility and defaecation conditions	Gastrointestinal disorders
10075246	Pseudoachalasia	Gastrointestinal dyskinetic disorders	Gastrointestinal motility and defaecation conditions	Gastrointestinal disorders
10073166	Pyloric sphincter insufficiency	Gastrointestinal atonic and hypomotility disorders NEC	Gastrointestinal motility and defaecation conditions	Gastrointestinal disorders
10037628	Pylorospasm	Gastrointestinal spastic and hypermotility disorders	Gastrointestinal motility and defaecation conditions	Gastrointestinal disorders
10066142	Sandifer's syndrome	Gastrointestinal atonic and hypomotility disorders NEC	Gastrointestinal motility and defaecation conditions	Gastrointestinal disorders

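### The SAP says the GI abdominal-related adverse event set leaves out oral and esophageal events, but the term list that implements it contains them

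*SAP*

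**What the plan says.** The point lies wholly within the SAP, which is written for study BCX7353-302. Section 10.1.2 introduces the event set in modest terms: "Gastrointestinal (GI) abdominal-related TEAEs are also of interest, although these are not TEAEs of special interest for investigator reporting purposes". It then makes three statements about what the set contains.

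- The rule: the events are "prospectively defined as all PTs within the MedDRA 19.1 hierarchy under the High-Level Group Terms (HLGTs", and it names two of these, GI signs and symptoms and GI motility and defecation conditions.
- The implementation: "See Section 17 for a detailed list of PTs, High Level Terms, and HLGTs".
- The rationale: the selection is broad enough to catch the relevant GI events, yet "excludes terms that, although in the GI SOC, are not representative of the events of concern such as oral or esophageal events".

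The Section 17 list includes, among others, "Oesophageal food impaction", "Oesophageal achalasia" and "Oesophageal spasm".

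Section 10.1.2 uses the set for separate listings, a nine-row summary by treatment group (any event, drug-related, Grade 3 or higher, leading to discontinuation or interruption, and so on), and Kaplan-Meier analyses of time to event and of duration. It also feeds a further analysis in which the number and proportion of subjects with "either a GI abdominal-related TEAE or an unconfirmed abdominal-only attack is presented".

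**The concern.** The rule and the list agree with each other, but the rationale contradicts both. Taking every PT under the two group terms brings in esophageal and swallowing terms, and no later step in the SAP takes them out. A programmer working from Section 17 and a reader relying on the sentence in Section 10.1.2 would understand different event sets.

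Two things are at stake. First, the overall GI abdominal summary, the Kaplan-Meier displays and the combined display would count events that the SAP itself says are not representative of the events of concern. Second, the study report could state that esophageal events were excluded when they were not. Section 10.1.2 stresses that the set was fixed in advance. Deciding after Part 1 unblinding which text governs would weaken that.

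**Working it through.** There is no figure in the plan to reproduce, so the check is a count of the Section 17 list set against the sentence in Section 10.1.2.

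**Size of the list.** 61 PTs under GI signs and symptoms + 44 under GI motility and defaecation conditions = 105.

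**Terms with oesophag in the name: 12.**
- Purely esophageal, 10: Oesophageal discomfort, food impaction, pain, achalasia, atony, hypomotility, motility disorder and spasm; Dyskinesia oesophageal; Presbyoesophagus.
- Gastro-oesophageal, 2: Gastrooesophageal reflux disease; Gastrooesophageal sphincter insufficiency.

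**Swallowing or oral terms by ordinary meaning: 3.** Dysphagia, Malignant dysphagia, Breath odour.

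**Arguably esophageal though not by name: 2.** Cardiospasm, Pseudoachalasia.

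**Totals under different readings.**
- Narrowest, purely esophageal by name: 10/105 = 9.5%.
- All terms with oesophag in the name: 12/105 = 11.4%.
- Clear conflict with the stated exclusion: 10 + 3 = 13, and 13/105 = 12.4%.
- Adding the four that need a decision (2 gastro-oesophageal + Cardiospasm + Pseudoachalasia): 13 + 4 = 17, and 17/105 = 16.2%.

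White nipple sign and Sandifer's syndrome were left out of every count because the documents do not establish their site.

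**By group term.** Of the 13 clear terms, 6 sit among the 61 under signs and symptoms (Oesophageal discomfort, food impaction and pain; Dysphagia; Malignant dysphagia; Breath odour). The other 7 sit among the 44 under motility, as do all 4 undecided terms. The conflict therefore does not come from one of the two group terms alone.

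**List after applying the stated exclusion.** 105 − 13 = 92 if all four undecided terms are kept; 105 − 17 = 88 if all are dropped.

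**Outputs fed by the list (Section 17.1).** Tables 14.3.1.29 to 14.3.1.39, 14.3.1.41 and 14.3.1.44 are 13 tables, each with an entire-study version, so 26. Listings 16.2.7.8 and 16.2.7.10 with entire-study versions make 4. Figures 14.3.1.40, 14.3.1.42 and 14.3.1.43 with entire-study versions make 6. In all, 26 + 4 + 6 = 36.

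**Scale of any effect.** With about 40 subjects per Part 1 group (Section 4.3.1), each subject whose only listed event is one of these terms moves that group's incidence by 1/40 = 2.5 percentage points. The documents do not say how many such subjects to expect, and the number may be zero.

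**The case against.** The strongest defence is that the operative definition is not ambiguous. All PTs under two named group terms is a reproducible rule, the list follows it, and only a sentence of rationale is wrong. That sentence might have meant merely that other oral or esophageal groupings in the GI system organ class were not selected. This stands in part: it shows that correcting the sentence alone is a legitimate repair. It does not remove the conflict, because the sentence as written says such events are excluded.

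A second defence is that the harm is limited. Tables 14.3.1.30 to 14.3.1.38 are broken down by PT and events are listed by subject, so esophageal terms would be visible. The same list applies to placebo and both doses. That is fair, but PT rows cannot simply be subtracted from an any-event count, since one subject may have several PTs. The overall summary, Kaplan-Meier and combined displays stay affected unless rebuilt from the listings.

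Several stronger readings are tempting, and the documents do not support them.

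- *A trial endpoint is distorted.* GI abdominal events are in none of the endpoint lists in Section 3.2. The endpoint named in Section 10.1.2 is drug rash.
- *Oral and throat events contaminate the set.* Only Breath odour is arguably oral. No listed PT names the mouth, lips, tongue or throat, and the High Level Term for abdominal pains is itself labelled as excluding oral and throat.
- *Incidence will be overstated by some number of points.* No reporting frequencies are given. The GI events described for this drug in Section 5.4.4.2 of the BCX7353-202 protocol are complaints such as nausea, dyspepsia, vomiting, diarrhea, flatulence and abdominal pain; reflux, dysphagia and esophageal events are not mentioned.
- *SAP Table 10 settles the matter because it files difficulty swallowing under airway symptoms.* That table classifies diary symptoms of attacks, not adverse event terms, and the attack side of the combined display is already restricted to abdominal-only attacks.

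**Conclusion.** The inconsistency is real. At least 10 of 105 PTs contradict the stated exclusion on the narrowest reading by name, 13 do on a plain reading, and up to 17 do if the four borderline terms are also judged esophageal. The counts beyond the names rest on the ordinary meaning of Dysphagia, Malignant dysphagia, Breath odour, Cardiospasm and Pseudoachalasia.

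The consequence is modest. It falls on a supplementary safety analysis, leaves hypothesis testing and the multiplicity scheme untouched, and matters numerically only if such events are reported. The SAP should still be corrected, because the written definition and the programmed one would otherwise differ in a set that is presented as prospectively fixed.

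**What to change.** Before Part 1 unblinding:

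1. Remove from the Section 17 list the 10 purely esophageal PTs, Dysphagia, Malignant dysphagia and Breath odour.
2. Record an explicit keep or drop decision, with a reason, for Cardiospasm, Pseudoachalasia, Gastrooesophageal reflux disease and Gastrooesophageal sphincter insufficiency.
3. Reword Section 10.1.2 so that the set is all PTs in the two group terms except those listed as excluded.
4. Program every GI abdominal table, listing and figure from the trimmed list.

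If the sponsor wants the full group terms, the alternative is to leave the list alone and delete the exclusion claim, so that the report does not say esophageal events were left out.

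The cost is one list edit and one sentence, or the sentence alone. No safety data are lost, since removed terms still appear in the general TEAE tables of Section 10.1.1.

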### 10.1.3. Missing and Partial Adverse Event Onset Dates

See Section 6.8.4.

### 10.1.4. Summaries of Adverse Event Incidence Rates per 100 Person-Years of Exposure to Study Treatment

For this study, the duration of exposure to study treatment will vary depending on whether the subject is initially assigned to placebo. Because of this, certain TEAE tables will be repeated using the number of TEAEs per 100 person-years of exposure instead of using a count, where 1 year = 365.25 days of exposure. These tables will not be created for the Part 1 primary efficacy analysis since the same amount of exposure is expected per treatment group for Part 1 analysis.

To determine the rate of TEAEs per person-year of exposure, the duration of treatment exposure will be computed for each subject and treatment. The rate of TEAEs per person-year will then
be calculated as the count of TEAEs divided by the duration of treatment exposure. This value will then be multiplied by 100 to compute the rate per 100 person-years of exposure. For subjects initially randomized to placebo, there will be exposure time for placebo treatment and a separate exposure time for treatment with either 110 or 150 mg. The total exposure for the treatment group of interest will sum the individual subject exposure time for each treatment group.

The following summary tables of rate of TEAEs per 100 person-years of exposure will be provided by treatment group (by SOC and PT):

- Summary of TEAE rate per 100 person-year of exposure
- Summary of drug-related, TEAE rate per 100 person-year of exposure
- Summary of TESAEs per 100 person-year of exposure

A listing of exposure to study treatment in 100 person-years will be provided by subject and treatment.

# **10.2.** Exposure to Study Treatment and Treatment Compliance

The number of subjects exposed to study treatment and the number of subjects who discontinue treatment early will be presented on the disposition table. A summary of exposure to study treatment will be also be presented and will include a summary of 100 person-years of exposure to study treatment as described in Section 10.1.4. Listings of exposure to study treatment and of drug accountability will be provided by subject and treatment. Kaplan-Meier plots of duration of study treatment will be provided. Treatment compliance will be computed based on drug accountability by determining the number of capsules taken relative to the number of capsules that should have been administered.

For compliance (%) for the study period of interest based on the drug accountability page of the eCRF:

Number of Capsules Taken = Number of Capsules Dispensed – Number of Capsules Returned

Expected Number of Capsules Taken  
= 
$$2 \times (Date of the Last Dose - Date of the First Dose + 1)$$

Treatment compliance based on dispensing information will be calculated for each study treatment that the subject received as follows:

Treatment Compliance (Dispensing) =  $\frac{Number \ of \ Capsules \ Taken}{Expected \ Number \ of \ Capsules \ Taken} \times 100$ 

Treatment compliance will be listed and summarized for Part 1 and overall for the entire study period at the time of the end of study analysis. For subjects initially assigned to placebo, treatment compliance will be computed for placebo treatment and separately for the active treatment received in Parts 2 and 3.

A categorical summary of treatment compliance will be produced with the following categories shown in Table 14.

Compliance	Range of Compliance (%)
Poor compliance	< 80%
Acceptable compliance	80% to < 90%
Good compliance	90% to 110%
Over-dosing	> 110%

Table 14:Definition of Compliance Categories

A plot of change from baseline attack rate by % compliance will be produced for Part 1, with treatment groups overlaid.

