#### Test product, dose and mode of administration:

BCX7353 capsules, to be administered orally.

BCX7353 capsules contain 55 and 75 mg of the active ingredient (free base equivalents). Subjects will take the following orally QD at approximately the same time each day, with whichever meal is typically the largest of the day:

Treatment Group 1 (110 mg QD) Parts 1 and 2: two 55-mg capsules of BCX7353 Treatment Group 2 (150 mg QD) Parts 1 and 2: two 75-mg capsules of BCX7353

Subjects randomized to Treatment Group 1 or 2 will receive the same dose in both Parts 1 and 2, for a total duration of 48 weeks of treatment during Parts 1 and 2 (24 weeks of treatment in each study part for Parts 1 and 2).

Subjects randomized to Treatment Group 3 (placebo) in Part 1 will be re-randomized to receive active study drug from the Week 24 visit (Part 2):

Treatment Group 3a (110 mg QD) Part 2: two 55-mg capsules of BCX7353

Treatment Group 3b (150 mg QD) Part 2: two 75-mg capsules of BCX7353

#### Part 3

BCX7353 capsules contain 110 and 150 mg of the active ingredient (free base equivalents). Subjects will take a single capsule orally once daily at approximately the same time each day, with whichever meal is typically the largest of the day.

Treatment Groups 1 and 3a (110 mg QD) Part 3: one 110-mg capsule of BCX7353

Treatment Groups 2 and 3b (150 mg QD) Part 3: one 150-mg capsule of BCX7353

Subjects randomized to Treatment Groups 1 and 2 will receive a total of up to 96 weeks of active BCX7353 treatment. Subjects randomized to Treatment Group 3 will receive a total of up to 72 weeks of active BCX7353 treatment.

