# Part 3 (48-week evaluation of safety of open-label BCX7353)

Part 3 of the study will start with the administration of the study drug dispensed at the Week 48 visit. Subjects will continue to receive the same BCX7353 dose in Part 3 to which they were randomized in Part 2 of the study in an open-label manner. Once Part 1 results are available, all subjects in Part 3 may be moved to a single dose level of BCX7353, based on the data from Part 1, if appropriate.

Study visits in Part 3 will occur during Weeks 60, 72, 84, and 96, with telephone contact at Weeks 52, 56, 64, 68, 76, 80, 88, and 92.

Subjects will continue to document all angioedema attacks that occur in a paper diary throughout Part 3 and will have regular visits to assess safety and tolerability. Investigator confirmation of attacks will not be required for Part 3. All attacks recorded by the subjects will be reviewed and confirmed or rejected according to a set of pre-defined rules prior to inclusion in effectiveness analyses. These rules, which were constructed in concert with HAE-treating physicians, will be outlined in this SAP.

A final study follow-up visit will be scheduled approximately 3 weeks following the last administration of study drug (Week 99).

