# 4.2. Definition of Study Drugs

BCX7353 110 mg QD is supplied as two 55-mg capsules of BCX7353 per dose for Parts 1 and 2 and as one 110-mg capsule of BCX7353 per dose for Part 3.

BCX7353 150 mg QD is supplied as two 75-mg capsules of BCX7353 per dose for Parts 1 and 2 and as one 150-mg capsule of BCX7353 per dose for Part 3.

Placebo QD is supplied as 2 capsules of matching placebo per dose.

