#### Table 4.Schedule of Assessments: Part 3 of Study BCX7353-302

Abbreviations: AE = adverse event; AE-QoL = Angioedema Quality of Life; CK-MB = creatine kinase MB isoenzyme; CRF = case report form;

ECG = electrocardiogram; EQ-5D-5L = EuroQoL 5-dimensional, 5-level questionnaire; NGAL = neutrophil gelatinase-associated lipocalin;

PD = pharmacodynamic; PK = pharmacokinetic; QoL = quality of life; QTcF = QT interval corrected using Fridericia's method; TSQM = Treatment Satisfaction Questionnaire for Medication; WPAI = Work Productivity and Activity Index.

a Period 3 study drug is to be initiated on Day 337, the day of the Week 48 visit.

b The Investigator (or designee) must call and talk to the subject during Weeks 52, 56, 64, 68, 76, 80, 88, and 92; alternative forms of interactive communication such as returned email and cellular text correspondence are acceptable. During all calls, the investigator (or designee) will assess the subject's overall wellbeing, and proper recording of attack details (if applicable).

- c Abbreviated physical examinations targeted to signs and symptoms will be performed at post-baseline visits.
- d At the Week 60, 72, and 84 visits, sites in Europe will dispense urinary pregnancy tests to subjects who are women of childbearing potential. These will be performed by the subject at home at Weeks 64, 68, 76, 80, 88, and 92.
- e To include blood pressure and pulse rate. Prior to obtaining vital signs, subjects should rest in a supine position for at least 5 minutes.
- f The protocol lists parameters to be assessed.
- g ECGs may be single assessments. Prior to obtaining an ECG, subjects should rest quietly in a supine position for at least 10 minutes. An ECG should be repeated for a change from baseline in QTcF > 60 msec or a QTcF interval > 500 msec.
- h Two EQ-5D-5L assessments will be administered at Weeks 60, 72, 84, and 96. The subject will fill out the first EQ-5D-5L to describe their current health state today as instructed per the instrument. The subject will also fill out a second EQ-5D-5L based on a recollection of their health state during an average attack that they experienced since the last study visit. If the subject has not had an attack since their last study visit, the subject is not required to fill out the second, attack-related EQ-5D-5L.

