- i Where possible, QoL and health outcome questionnaires should be collected as the first assessments at a visit.
- j Any issues (including mediocre or poor compliance) warranting diary re-education should occur on an as-needed basis.
- k Any time the diary is in the subject's possession after Week 48 the subject will enter HAE attacks and relevant details at least once per day. No dosing information will be collected in in subject diaries in Part 3.
-  Study drug should be taken at approximately the same time each day, with whichever meal is typically the largest of the day. Subjects are not required to take their doses at clinic visits.
- m Early termination visit only (if occurring during dosing phase).
- n PK and PD blood samples will be drawn on all subjects with no particular relationship to the timing of study drug dosing. The Investigator (or designee) must ensure that the time of the last dose prior to PK and PD draw is recorded in the subject's diary (this may also be captured in the CRF).

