#### 17. **APPENDIX**

# **17.1.** Table of Contents for Data Display Specifications

Output #	Population	Output Title
14.1.1.1	ITT	Summary of Subject Disposition by Country and Site, Part 1
14.1.1.1.ES	ITT	Summary of Subject Disposition by Country and Site, Entire Study
14.1.2.1	ITT	Summary of Analysis Populations
14.1.2.2	ITT	Summary of Subgroups
14.1.2.3.1	ITT	Summary of Inclusion/Exclusion Criteria Deviations
14.1.2.3.2	Screen Failures	Summary of Inclusion/Exclusion Criteria Deviations
14.1.2.4	ITT	Summary of Protocol Deviations, Part 1
14.1.2.4.ES	ITT	Summary of Protocol Deviations that Occurred During Part 2
14.1.2.5	ITT	Summary of Confirmation of Diagnosis of HAE Type I or II
14.1.3.1.1	ITT	Summary of Demographic Characteristics
14.1.3.1.1.ES	ITT	Summary of Demographic Characteristics - Subjects Who Transitioned to Part 2
14.1.3.1.2	РР	Summary of Demographic Characteristics
14.1.3.1.3	Screen Failures	Summary of Demographic Characteristics
14.1.3.2	ITT	Summary of Subject-Reported HAE Baseline Characteristics - HAE Medical History
14.1.3.3	ITT	Summary of Past Prophylactic Treatments of HAE
14.1.3.4	ITT	Summary of Current On-Demand Treatments of HAE
14.1.3.5	ITT	Summary of Subject-Reported HAE Baseline Characteristics – Primary Acute Attack Treatment Information
14.1.3.6	ITT	Summary of Pre-Treatment Investigator-Confirmed Attack Rates and Angioedema Symptoms
14.1.4.1	ITT	Summary of Medications Taken within 30 Days of Screening and Discontinued Prior to Dosing
14.1.4.2	ITT	Summary of Concomitant Medications, Part 1
14.1.4.2.ES	ITT	Summary of Concomitant Medications – Entire Study
14.1.4.3	ITT	Summary of Concomitant Medications for HAE, Part 1
14.1.4.3.ES	ITT	Summary of Concomitant Medications for HAE, Entire Study
14.1.4.3.P3	ITT	Summary of Concomitant Medications for HAE, Part 3
14.1.4.4	ITT	Summary of Concomitant Medications for HAE – Attack Level, Part 1
14.1.4.4.ES	ITT	Summary of Concomitant Medications for HAE – Attack Level, Entire Study
14.1.4.4.P3	ITT	Summary of Concomitant Medications for HAE – Attack Level, Part 3
14.1.5.1	Safety	Summary of Treatment Exposure and Treatment Compliance, Part 1
14.1.5.1.ES	Safety	Summary of Treatment Exposure and Treatment Compliance, Entire Study
14.2.1.1	ITT	Summary of Hierarchical Testing for Efficacy Endpoints
14.2.1.2.1	ITT	Overall Attack Summary During Part 1
14.2.1.2.1.ES	ITT	Overall Attack Summary During Entire Study
14.2.1.2.2	РР	Overall Attack Summary During Part 1

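### SAP 10.2 expects two capsules a day throughout, but Part 3 is one a day, so fully adherent 96-week completers score 75.0% or 66.7% and are classed as poorly compliant

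*SAP*

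**What the plan says.** SAP 10.2 computes compliance as capsules taken divided by capsules expected, times 100. Capsules taken is a raw count, dispensed minus returned. Capsules expected is "2 \times (Date of the Last Dose - Date of the First Dose + 1"), and the section applies this to whichever study period is being reported. Compliance is to be listed and summarized for Part 1 and for the whole study. For subjects first assigned to placebo, "treatment compliance will be computed for placebo treatment and separately for the active treatment received in Parts 2 and 3". Table 14 then classes the result: below 80% poor, 80% to below 90% acceptable, 90% to 110% good, above 110% over-dosing. SAP 17.1 lists the end-of-study output as "Summary of Treatment Exposure and Treatment Compliance, Entire Study" (14.1.5.1.ES).

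The dosing schedule is given elsewhere. SAP 4.2 states "BCX7353 110 mg QD is supplied as two 55-mg capsules of BCX7353 per dose for Parts 1 and 2 and as one 110-mg capsule" per dose in Part 3, and gives the same pattern for 150 mg. The Technical Summary Report says of Part 3: "Subjects will take a single capsule orally once daily at approximately the same time each day". Placebo, given in Part 1 only, is two capsules per dose.

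**The concern.** A fixed multiplier of 2 matches the schedule in Parts 1 and 2 and is double the schedule in Part 3. Because the numerator counts capsules rather than milligrams, it cannot absorb the change of capsule strength. Every compliance figure that includes Part 3 days is therefore too low.

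Part 3 exists mainly to describe long-term safety, and adherence is basic context for reading those data. As specified, the final table would show fully adherent long-term subjects as poorly compliant. It would also show an artificial gap between subjects who started on active drug and those who came from placebo. Table 4 adds that "No dosing information will be collected in in subject diaries in Part 3", so diary dosing records cannot be used to correct the figure for that period.

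**Working it through.** **Inputs**
- Durations (Technical Summary Report, duration of treatment): 24 + 24 + 48 weeks = 168 + 168 + 336 = 672 days. Active treatment after placebo is 24 + 48 = 72 weeks = 504 days.
- Part 3 start (Table 4, footnote a): "Period 3 study drug is to be initiated on Day 337, the day of the Week 48 visit".
- Capsules per day (SAP 4.2): 2 in Parts 1 and 2, 1 in Part 3.

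The SAP states no compliance percentage to reproduce. As a check, the formula does return 100% under perfect adherence where two capsules a day are taken: 336/336 in Part 1 and 672/672 over Parts 1 and 2.

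**Perfect adherence to the end of Part 3**

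| Subject | Capsules taken | Expected under SAP 10.2 | Compliance |
|---|---|---|---|
| Active from Day 1 | 2×336 + 1×336 = 1008 | 2×672 = 1344 | 75.0% |
| Ex-placebo, active treatment (Parts 2 and 3) | 2×168 + 1×336 = 672 | 2×504 = 1008 | 66.7% |
| Part 3 days alone | 336 | 2×336 = 672 | 50.0% |

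The first two rows are the figures SAP 10.2 asks for, and both are below 80%. Moving the Part 3 start (Day 330 to 343) and the last dose (Day 664 to 680) across the protocol windows for Weeks 48 and 96 in Table 9 gives 74.2% to 75.8% and 65.7% to 67.5%.

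**When the category changes.** After x days of Part 3 with perfect adherence:
- Active from Day 1: (672 + x) / [2(336 + x)]. This is at least 0.90 while 67.2 ≥ 0.8x, so x ≤ 84. It is at least 0.80 while 134.4 ≥ 0.6x, so x ≤ 224.
- Ex-placebo: (336 + x) / [2(168 + x)]. This is at least 0.90 while 33.6 ≥ 0.8x, so x ≤ 42. It is at least 0.80 while 67.2 ≥ 0.6x, so x ≤ 112.

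A subject who leaves Part 3 early may therefore keep the right category, although the percentage is already too low.

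**What the Table 14 cut-offs mean for a completer.** Multiply by 1344/1008 or 1008/672 to convert to percent of the true schedule:

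| Cut-off in Table 14 | Active from Day 1 | Ex-placebo |
|---|---|---|
| 80% | 106.7% | 120.0% |
| 90% | 120.0% | 135.0% |
| 110% | 146.7% | 165.0% |

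A completer is labelled good only when the capsule count already exceeds 110% of schedule. A count at twice the Part 3 schedule would score 1344/1344 or 1008/1008 = 100%, when the true figures are 1344/1008 = 133.3% and 1008/672 = 150.0%. Whether that many capsules would be dispensed is not stated.

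**Dose-level change.** SAP 4.1 says "subjects in Part 3 may be moved to a single dose level of BCX7353". If that happened at Part 3 entry and the new level were scored as its own treatment, perfect adherence to it would score 336/672 = 50%.

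**The case against.** The strongest reply is that this is a drafting slip of limited consequence. The sentence before the formula in SAP 10.2 states the right principle: capsules taken against capsules that should have been given. No endpoint, population membership or test uses the Part 3 figure. Drug accountability is listed for the entire study (16.2.5.1.ES), so a reader could recompute compliance. A cluster of completers near 75% and 67% would probably be noticed at output review.

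The limited scope stands. The rest explains how the error might be caught but does not remove it. A programmer follows the formula, and SAP 6.4 treats a true difference in method or data handling as something to document, so a silent correction would itself depart from the plan.

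Three narrower points also stand. The over-use and dose-change scenarios are conditional: SAP 4.1 does not say that a dose change would come at Part 3 entry. SAP 17.1 lists some per-protocol outputs beyond Part 1, although SAP 7.3 confines per-protocol analyses to Part 1. Membership of that population is unaffected either way, because SAP 6.5.4 bases it on completing Part 1 and on major deviations, and SAP 7.3 says Part 2 and 3 deviations do not exclude subjects. Finally, the protocol supplied is for study BCX7353-202 while this SAP is for BCX7353-302, and the table shells are held separately. The absence of a Part 3 multiplier can therefore be confirmed only for the SAP.

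**Conclusion.** The point holds: the expected-capsule formula in SAP 10.2 contradicts the Part 3 schedule in SAP 4.2 and the Technical Summary Report. Perfectly adherent 96-week completers would be reported at 75.0% (active start) or 66.7% (active treatment after placebo) and classed as poorly compliant. These figures assume uninterrupted Parts of 168, 168 and 336 days; visit-window shifts do not change the category.

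The effect is confined to the entire-study compliance summary, listing and categories, including the Parts 2 and 3 active-treatment figure for ex-placebo subjects. Part 1 compliance, the Part 1 plot of attack rate against compliance, per-protocol membership and all hypothesis tests are unaffected. It should be corrected before the end-of-study outputs are programmed, but it does not threaten the trial's main conclusions.

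**What to change.** Replace the single formula with one computed for each Part and each treatment received:

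expected capsules = scheduled capsules per day (2 in Parts 1 and 2, 1 in Part 3, from SAP 4.2) × (last dose date − first dose date + 1, within that Part and treatment).

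Sum over the Parts in the reporting period. Keep placebo and active treatment separate for ex-placebo subjects, and treat a change of dose level in Part 3 as a separate treatment. Apply Table 14 to capsules taken divided by that sum. Perfect adherence then gives 1008/(2×336 + 1×336) = 100% and 672/(2×168 + 1×336) = 100%.

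The cost is one SAP formula and one derivation, with no change to conduct. It needs first and last dose dates by Part and treatment. SAP 6.6 says the first Part 2 dose is recorded in the eCRF. The SAP does not say so for Part 3, but SAP 6.7.5.1 already ends Part 2 at the first Part 3 dose, so that time point has to be available. If it is not recorded directly, the Week 48 visit date could stand in, stated as an assumption.
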